3.2. Inclusion and Exclusion Criteria

3.2.1. Inclusion Criteria

- Age \geq 21 years on date of consent
- Optimal pharmacologic therapy is defined by published guidelines from the American Heart Association and the American College of Cardiology
- Existing indication for CRT device with initial implant scheduled within 1 calendar month on or from date of randomization
- Ischemic or nonischemic cardiomyopathy
- LVEF \leq 35% within 12 calendar months prior to or on consent date by angiographic, radionuclide, or echocardiographic methods
- NYHA class II-IV (ambulatory) on consent date
- QRS \geq 120 ms for LBBB and \geq 150 ms for non-LBBB patients within 1 calendar year prior to or on consent date
- Continuous AF $>$ 3 calendar months when no further efforts to restore sinus rhythm are feasible or pursued**

***ECG evidence of AF will be required at enrollment and at 2 additional time points, one within 3 calendar months and one \geq 3 calendar months prior to enrollment, with no intervening ECGs revealing sinus rhythm and/or no successful effort to restore sinus rhythm for $>$ 24 hours*

OR

- Active CRT-D device implanted within the last calendar year with $<$ 15% improvement in LVSEV from pre-implant cardiac imaging. The evaluation of LVSEV post implant must be within the last three calendar months.
- Continuous AF $>$ 3 calendar months when no further efforts to restore sinus rhythm are feasible or pursued (see definition above)

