Randomization as a method of experimental control has been extensively used in human clinical trials. It prevents the selection bias and insures against accidental bias. It produces the comparable groups and eliminates the source of imbalance after treatment assignment. Finally, it permits the use of probability theory to express the likelihood of chance as a source for the difference of the final outcome. Randomization in this study will occur at visit 2. It should be noted that that visit 2 could take place on the same day as visit 1 and visit 3.

1. CRT-D device implantation or
2. CRT-D device implantation and AVJ ablation procedure

For subjects with an existing CRT-D device

1. Ablation
2. Medical management

Subjects will be notified that randomization is part of this study during the consent process. Subject will be informed which randomized arm they have received after completing the quality of life questionnaire. Subject will be notified that either treatment arm may be less or more effective, or may have more or less side effects.

Randomization will be stratified by enrolling site and generated per the scheme described in Section 11. The randomization strings for treatment assignment will be provided to the database programmer at the coordination site by chief statistician [name] and uploaded in the electronic data capture system with appropriate testing and validation that the system is working correctly prior to the beginning of subject

randomization. The enrolling site has full responsibility for completion of the CRFs required for subject randomization. The enrolling site may contact the data center project manager and will notify about randomization results only if the enrolling site has no internet access or the web base program will automatically assign the randomization treatment assignment and subject ID based on the randomization strings provided by the biostatistician. The randomization result is viewed by the enrolling site in the eDC system following randomization or documented on the paper CRF which is returned to the enrolling site if randomization cannot be done through the eDC system. All eligibility criteria will be confirmed prior to providing the randomization treatment assignment/subject ID to the enrolling site.

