5.3. Visit 1: Screening

- Potential subjects will be screened to determine eligibility for participation in the study per medical record review. Potential subjects will be identified based on planned CRT-D implant or existing active CRT-D device. Those who fulfill the study eligibility criteria and current indication for CRT-D implantation or existing active CRT-D device can be approached for informed consent, but additionally ECG evidence of AF will be required at consent and meet study criteria prior to patient randomization. The screening visit might occur on the same day as the Baseline and procedure visit described below.

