5.4. Visit 2: Randomization and Baseline Assessment

The following tasks will be performed and documented at the Visit 2 (Visit 2 could take place on the same day as Visit 1 and Visit 3) following informed consent:

- Reconfirm inclusion and exclusion criteria prior to randomization. Presence of AF in potential subjects who qualify for CRT-D implantation or existing CRT-D device will be confirmed as follows: AF present at screening visit and at 2 additional time points, one within 3 months and one ≥ 3 months prior to enrollment, with no intervening ECGs revealing sinus rhythm and/or no successful effort to restore sinus rhythm for > 24 hours.
- Subjects will undergo an echocardiogram at Baseline Visit prior to CRT-D implantation if no echocardiogram was performed within the past calendar year prior to randomization to qualify patient for CRT-D implant per current medical guidelines. For subjects with an existing CRT-D device, an echocardiogram demonstrating <15% change in LVSEV in comparison to pre-implant cardiac imaging must be within three calendar months prior to consent.

- Perform randomization to AVJ ablation or conventional treatment without ablation if potential subject meets as study eligibility criteria via the electronic data capture system or manually if internet access is not possible.

Note: Some of the following data will be required to confirm study eligibility criteria and recorded at time of screening confirmation and randomization. If not required to confirm study eligibility, this data will be recorded after randomization occurs.

- Perform clinical assessment and collect data on current prescribed CV medications
- Complete limited physical examination including vital signs, body weight, and height
- Perform symptom assessment
- Obtain a copy of standard 12-lead ECG used to confirm study eligibility
- Obtain most recent echocardiogram images obtained within 1 calendar year prior to or on randomization date used to determine study eligibility and prior to CRT-D implant
- Quality of Life assessment (prior to providing randomized treatment assignment to subject)

5.5. **Visit 3: Procedure Day(s)**

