11. STATISTICAL METHODS AND POWER CONSIDERATIONS

Overall Study Design and Primary Endpoint: This study is designed as a 2-arm unblinded randomized clinical trial. A total of 40 subjects receiving CRT-D will be randomized 1:1 to AVJ ablation or control arm (without AVJ ablation), stratified by enrolling site. The primary endpoint is the binary response defined as $\geq 15\%$ reduction in LVESV from baseline to 6 months.

Randomization Scheme: Enrolled subjects will be 1:1 randomized to AVJ ablation (with CRT-D) or control (CRT-D only). The randomization sequence will consist of a string of random 4- and 6-blocks. That is, there will be a 50% chance that the first block will consist of 4 subjects (2 AVJ ablation + 2 control, in random order), and a 50% chance that it will contain 6 subjects (3 AVJ ablation + 3 control, in random order). Each subsequent block will similarly be of random size. This procedure makes it very difficult for anyone to predict whether the next treatment assignment will be AVJ ablation (or control), helping to ensure integrity of the study. In contrast, if each block were of size 4, then it would be trivial to perfectly predict every 4th treatment assignment as well as the 3rd, if the first two were both AVJ ablation or both control, which would be undesirable. Randomization will be stratified by enrolling site. The randomization scheme will be generated by chief statistician [name] and provided to the CDC per Section 5.

Endpoint: The primary endpoint is the binary response defined as $\geq 15\%$ reduction in LVESV from baseline to 6 months.

Power and Sample Size: Randomizing 20 subjects per arm (for a total of 40 subjects), and allowing for up to 10% drop-out due to withdrawal, death, or inadequate imaging, we expect at least $n=18$ evaluable subjects per arm. This sample size will provide 80% power to detect an absolute change of 50% in response rates, using a 0.05 level 2-sided Fisher exact test, assuming the actual response rate in the AVJ ablation arm is 80-85%, as in

Gasparini 2006 (1) and Ferreira 2008 (6), where the empirical change in response rates was $\Delta = 49\%$ and 33% , respectively.

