Crossovers: We anticipate that virtually no subjects will cross over from the AVJ ablation arm to the control arm. We expect at most 2-5% crossovers from control to the AVJ ablation arm, but we will work with investigators to consider these crossovers ideally only after trial completion so that they would have no effect on the primary endpoint. In any case, since the primary analyses will be conducted on an intention to treat (ITT) basis, crossovers will not affect the primary analysis. Furthermore, the stated response rates pertain to the planned ITT analyses, so they and the associated power computations already implicitly account for the small expected effect of the limited crossovers we anticipate for this study.

Statistical Methods: The primary analysis will be an intention-to-treat (ITT) analysis based on Fisher's exact test of the null hypothesis that the response rates are identical for both arms, conditional on the total number of responders. Response rates for each arm will be estimated by the empirical proportions (maximum likelihood estimates), along with associated Clopper-Pearson exact 95% confidence intervals (CI). Maximum likelihood estimates and associated 95% CI for the odds ratio (OR), relative risk (RR), and the absolute change in proportions will be used to summarize the treatment effect.

Secondary Analyses: Secondary endpoints include: a) change in LVEF from baseline to 6 months; b) LV end diastolic volume and change from baseline to 6 months; c) HF event including repeated HF events; d) all-cause mortality; e) VT/VF arrhythmic events requiring ICD therapy; f) inappropriate ICD therapy; g) percentage BiV pacing; h) quality of life; and i) complications related to AVJ ablation procedure. Since power for analyzing most secondary endpoints will be limited, secondary analyses will be mainly descriptive in nature. However, to the extent feasible, statistical analysis will be performed, as described briefly below.

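### Cheap improvement: entry route (first CRT-D implant or existing CRT-D with poor volume response) is neither a randomization stratum nor used in the primary estimate, and no result by route is planned

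*Combined protocol and SAP*

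**What the plan says.** **Two entry routes.** Section 3.2.1 joins two sets of criteria with an OR. The first is a planned initial implant. The second is "Active CRT-D device implanted within the last calendar year with" less than 15% volume improvement since before implant. (The plan writes LVSEV there; I read it as left ventricular end-systolic volume.) Section 5.1 lists the arms separately: "For subjects with an existing CRT-D device" they are ablation or medical management, while first-implant subjects receive a CRT-D with or without ablation.

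**Randomization.** Section 11 says: "Randomization will be stratified by enrolling site". The blocks are of random size 4 or 6. Section 5.1 names the same single stratum. Section 3.1 plans 40 subjects at 20 to 40 sites.

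**Primary analysis.** The endpoint is a reduction in LVESV of at least 15% at 6 months. The analysis is Fisher's "exact test of the null hypothesis that the response rates are identical for both arms, conditional on the total number of responders". The effect is summarized without adjustment: "Maximum likelihood estimates and associated 95% CI for the odds ratio (OR), relative risk (RR), and the absolute change in proportions will be used". Covariate adjustment appears only in the linear models for continuous secondary endpoints, which name baseline values and demographics. Section 11 plans nothing by route.

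**Route is known in time.** Section 5.3 says: "Potential subjects will be identified based on planned CRT-D implant or existing active CRT-D device". For existing-device subjects, Section 5.4 requires "an echocardiogram demonstrating <15% change in LVSEV in comparison to pre-implant cardiac imaging" before consent. Section 5.1 says that "the web base program will automatically assign the randomization treatment assignment and subject ID based on the randomization strings".

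**The concern.** Three features of the design make route plausibly prognostic for the primary endpoint:

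- Existing-device subjects are selected for missing a 15% volume threshold while on CRT, and the endpoint is a 15% volume threshold.
- Their qualifying echocardiogram is post-implant, whereas the first-implant baseline precedes CRT.
- Their controls start no new device therapy, whereas first-implant controls start CRT. A control response therefore means different things in the two routes.

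At stake are precision and readability. A chance excess of one route in one arm moves the observed difference, and the planned output would neither correct this nor show it. Section 2.2 wants the pilot as proof of concept for a more definitive study. For that purpose it matters whether responders were first implants, earlier non-improvers or both.

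**Working it through.** **1. The plan's own figure.** Inputs from Section 11: 20 randomized per arm, 10% drop-out, so 20 × 0.90 = 18 evaluable per arm; two-sided 0.05 Fisher test; 80–85% in the ablation arm and a 50-point difference. Exact enumeration over two binomials gives power of 83.5% (80 vs 30), 83.8% (82.5 vs 32.5) and 84.2% (85 vs 35). With 17 per arm it is 79.2%, 79.5% and 80.1%. The stated 80% holds.

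**2. What site strata deliver.** The average is 40/40 = 1 to 40/20 = 2 subjects per site. If accrual is random over S sites, the share of subjects at a site with four or more is P(Binomial(39, 1/S) ≥ 3): 31% for 20 sites, 14% for 30, 7% for 40. Most blocks never fill.

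**3. Chance imbalance by route.** The route mix is assumed. The figures are the between-arm difference in existing-device share, in points, from simulated 4/6 blocks.

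| Existing-device subjects | Site strata: median / 95th percentile | Route strata: median / 95th percentile |
|---|---|---|
| 8 of 40 | 8 / 25–26 | 0 / 8 |
| 16 of 40 | 11 / 30–32 | 0 / 6 |
| 20 of 40 | 10 / 30–31 | 0 / 5 |

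Check: with exactly 20 per arm and 16 of 40, the hypergeometric probability of a difference of at least 20 points is 33%, and of at least 30 points about 11%.

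**4. Effect on the estimate.** Let d be ablation share minus control share, and g_A and g_C the existing-minus-new response gaps in the two arms. With equal arms the shift is (d/2)(g_A + g_C). At d = 30 points:

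- 40-point gap in both arms: 0.15 × 80 = 12 points.
- 40-point gap in controls only: 0.15 × 40 = 6 points.
- Controls 30 lower, ablation 20 higher: 0.15 × 10 = 1.5 points.

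At the median d of about 11 points the first two are about 4 and 2. The SD of the difference is √[(0.8×0.2 + 0.3×0.7)/18] = 0.143, or about 14 points.

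**5. Power.** Simulated at 80% vs 30% overall, 40 randomized, 36 evaluable, two-sided 0.05. The stratified exact test sums ablation responders over routes and conditions on each route's margins. Simulation error is about 0.2–0.4 points. The range under the current plan is over site patterns. The reversed gap is controls 30 points lower and ablation 20 points higher in existing-device subjects.

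| Mix | Assumed gap | Current plan | Fisher, route strata | Stratified exact test, route strata |
|---|---|---|---|---|
| 16/40 | none | 84.4–85.3% | 85.0% | 85.2% |
| 16/40 | controls only, 30 | 84.4–85.5% | 85.6% | 86.5% |
| 16/40 | controls only, 40 | 84.8–85.7% | 85.8% | 86.9% |
| 16/40 | both arms, 20 | 84.0–85.1% | 85.4% | 86.8% |
| 16/40 | both arms, 30 | 84.2–84.8% | 85.9% | 88.8% |
| 16/40 | both arms, 40 | 83.7–84.8% | 86.7% | 92.8% |
| 16/40 | reversed | 85.4–85.9% | not run | 85.5% |
| 8/40 | none | 84.6–84.9% | 85.0% | 84.8% |
| 8/40 | controls only, 30 | 84.5–84.9% | 85.6% | 85.5% |
| 8/40 | both arms, 30 | 83.9–85.0% | 85.6% | 87.3% |
| 8/40 | reversed | 85.0–85.7% | not run | 84.8% |

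A separate run (30 sites, 16/40) gave 84.7% to 84.8% (none), 84.4% to 85.9% (controls only, 30), 85.0% to 89.2% (both, 30) and 85.9% to 85.9% (reversed).

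**6. Precision and level.** At 16/40 the SD of the risk difference, current unadjusted to Mantel-Haenszel with route strata, goes from 0.145 to 0.143 (none), 0.142 to 0.137 (controls only, 40), 0.145 to 0.136 (both, 30) and 0.138–0.140 to 0.138 (reversed). With 50% response in both arms, type I error was 3.4–3.8% for Fisher under site strata, 2.3–3.5% for Fisher under route strata and 3.0–3.6% for the stratified exact test. All are below 5%.

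**The case against.** The case for leaving the plan alone is substantial. An unadjusted randomized comparison is legitimate in a 40-subject pilot, and its confidence interval already carries chance imbalance. The larger power gains need existing-device subjects to respond much worse under ablation too. The clearest mechanism in the documents, controls who start no new device, supports only a controls-only gap. The trial's premise also allows the reverse: if CRT failed for want of effective pacing, earlier non-improvers might do better with ablation, and then there is no gain. All of this stands.

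A reader might also infer that the stratified exact test should replace Fisher's test as primary. The figures do not support that. On the current allocation with 8 of 40 existing-device subjects, the stratified test alone loses 1.3–1.5 points with no gap and 1.8–2.0 with a 30-point controls-only gap. With the reversed gap it loses about 2 points (16/40) to 3.5 (8/40).

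Finally, by-route counts will be thin. At 8/40 there are about 8 × 0.9 = 7 evaluable existing-device subjects, three or four per arm, and 2 of 4 responders has an exact 95% interval of about 7–93%. That limits the table to description. It does not remove its use: under the reversed gap the treatment effect would differ between routes by 20 + 30 = 50 points, and the pooled analysis would show nothing of it.

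**Conclusion.** The point stands as a cheap improvement, not an error. The documents do not support reading it as an invalid or biased primary test: randomization protects the level, and the unadjusted difference is right on average. Nor do they support reading the trial as underpowered because of pooling, since the stated 80% is met in every 80% vs 30% scenario in the table.

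The power gain from route strata plus a stratified exact test is about 0 with no gap, 0 to 2 points with a controls-only gap, about 4 to 5 with a 30-point gap in both arms at 16/40, and about 0 if the ablation gap is reversed. The 8 to 9 points seen with a 40-point gap in both arms should not be expected. That case assumes 96% vs 56% under ablation and 46% vs 6% in controls. These gains also belong to the stratified test; with Fisher kept as primary, the comparable gain is about 0 to 3 points.

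The main benefits are therefore protection against route imbalance (95th percentile of about 30 points reduced to about 6 at 16/40) and a result readable by route. Route mix and gaps are assumptions throughout.

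**What to change.** (a) In Section 11, and in the two places in Section 5.1 that name site as the stratum, replace site strata with central random 4/6 blocks stratified by device status at eligibility (new implant or existing CRT-D). Adding route within site would not work at one or two subjects per site.

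(b) Keep Fisher's exact test and the planned unadjusted estimates as primary. Pre-specify as a sensitivity analysis a route-stratified exact test and a Mantel-Haenszel risk difference, Σw_k d_k / Σw_k with w_k = n_Ak n_Ck / n_k over routes k, with a named 95% CI method. The Sato variance is one option: simulated coverage was 92–94%, against 92–93% for an unadjusted Wald interval. Report responders over evaluable subjects by arm within each route, descriptively.

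If randomization cannot be changed, do (b) only.

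Cost: no added subjects, visits or data. Nominal site balance is given up, though these blocks barely deliver it. The electronic lists must be rebuilt and re-validated. The link between randomization strings and subject ID needs checking, because Section 5.2 builds the ID from site number and subject number within site. The by-route cells will be small.

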12. ORGANIZATION OF THE STUDY

The organization structure of this small pilot trial is based on collaboration between [name] serving as overall PI being in charge of site and subject recruitment with Drs. [name] as Co-PI, who will ensure coordination of the trial utilizing infrastructure successfully developed at the Heart Research Follow-up Program at University of Rochester Medical Center, Rochester, NY. Serving as the CDC the University of Rochester will be responsible for overall study management, data management, data reporting and center communications for the study. The University of Rochester will also be responsible for other project management tasks.

The University of Rochester Heart Research directed by [name] and his team has developed a limited access electronic data capture (EDC) web-based management system for several past and ongoing studies located on a production server hosted by the University of Rochester. The system integrates subject enrollment from enrolling sites, randomization, follow-up, invoicing, and core lab and endpoint adjudication committees with confidentiality as described in Section 10. Manual and/or automatic queries will be created in the EDC system and will be issued to the site for appropriate response. Enrolling site staff will be responsible for resolving all queries in the database, in a timely manner. The enrolling site principal investigator (PI) provides his/her electronic signature on the appropriate electronic case report forms (eCRFs) in compliance with local regulations. Changes to data previously submitted to the sponsor require a new electronic signature by the PI acknowledging and approving the changes. Database backups are performed regularly.

The Principal Investigator of an Enrolling site is responsible for ensuring that the study is conducted in accordance with the protocol and ethical principles that have their origins in the Declaration of Helsinki, any conditions of approval imposed by the reviewing IRB/EC, and prevailing local laws and/or regulations, whichever affords the greater protection to the subject.

The Principal Investigator's responsibilities include, but are not limited to, the following:

- Prior to beginning the study, sign the Clinical Study Agreement documenting his/her agreement to conduct the study in accordance with the protocol.
- Provide his/her qualifications and experience to assume responsibility for the proper conduct of the study and that of key members of the center team through up-to-date curriculum vitae or other relevant documentation and disclose potential conflicts of interest, including financial, that may interfere with the conduct of the clinical study or interpretation of results.
- Make no changes in or deviate from this protocol, except to protect the life and physical well-being of a subject in an emergency; document and explain any deviation from the approved protocol that occurred during the course of the study.
- Create and maintain source documents throughout the clinical study and ensure their availability with direct access during monitoring visits or audits; ensure that all clinical-investigation-related records are retained per requirements.
- Ensure the accuracy, completeness, legibility, and timeliness of the data reported to the CDC in the CRFs and in all required reports including query resolution and event source documentation. At completion of the study the Principal Investigator will be responsible for approval of the data collected via electronic signature of all CRFs.
- Record, report, and assess (seriousness and relationship to the subject condition/device/procedure) every adverse event per the protocol definition to the CDC and local reporting requirements as well as supply the CDC/IRB with any additional requested information related to the safety reporting of a particular event
- Allow and support regulatory authorities and the IRB/EC when performing auditing activities if needed.
- Ensure that informed consent is obtained in accordance with applicable laws, this protocol and local IRB/EC requirements.
- Make all reasonable efforts to avoid subject withdrawal prior to 6 months and ascertain the reason(s) for a subject's premature withdrawal from clinical investigation while fully respecting the subject's rights.

- Ensure that an adequate investigation site team and facilities exist and are maintained and documented during the clinical investigation.
- Ensure appropriate training requirements are met and adequate supervision of those to whom tasks are delegated. The investigator is accountable for regulatory violations resulting from failure to adequately supervise the conduct of the clinical study.
- Prior to gaining Approval-to-Enroll status, PI will provide to the CDC documentation verifying that their IRB/EC is registered or that registration has been submitted to the appropriate agency, as applicable according to national/regulatory requirements. A copy of the written IRB/EC approval and approved Informed Consent Form must be received by the CDC before recruitment of subjects into the study. Prior approval must also be obtained for other materials related to subject recruitment or which will be provided to the subject.
- Obtain Annual IRB/EC approval and renewals throughout the duration of the study as required by local IRB/EC requirements. Copies of the IRB/EC continuance of approval must be provided to the CDC.

